6.2.9 Subgroup analysis

Patients with actual qualifying revascularization procedure

In addition to the stratification based on the IxRS assignment, the study will be analyzed based on the actual qualifying revascularization procedure and actual clopidogrel use in relation to qualifying revascularization as follows:

Statistical Analysis Plan

Protocol No.: **BAY 59-7939 / 17454**

Page: 24 of 36

- surgical,
- endovascular including hybrid with clopidogrel,
- endovascular including hybrid without clopidogrel.

Patients with hybrid procedures are classified as endovascular revascularization. We plan to determine the treatment effect among patients in each of the above strata (actual classification). Treatment groups will be compared using Cox proportional hazards model with treatment as a covariate for the primary (also the individual components) and secondary efficacy endpoints, using the ITT analysis set and ITT data scope. The point estimate and corresponding 95% CI for the hazard ratio (HR, rivaroxaban added to ASA vs. ASA alone) will be reported. Additional analyses on other endpoints may be performed based on both per IxRS assignment and actual type of qualifying procedure and clopidogrel use.

Other subgroups

The analyses for the other subgroups (as defined in section 6.2.4) will be performed based on the same analysis sets and data scopes as in the main analyses for the primary efficacy outcome (also the individual components). The results will be presented descriptively (and with forest plots). The hazard ratio for the treatment effect will be estimated separately within each level of a subgroup variable using the Cox proportional hazards model stratified by type of procedure and clopidogrel use (per IxRS assignment) (except for subgroups related to qualifying revascularization procedure or clopidogrel use) with treatment as a covariate.

Additionally, homogeneity of treatment effect in subgroups, both in magnitude and direction, will be assessed by adding a covariate for the subgroup variable and the corresponding treatment-subgroup interaction to the respective Cox proportional hazards model. This further investigation includes the likelihood ratio test proposed by Gail to test for qualitative interaction (Gail et al. 1985).

As the number of subgroup analyses may be large, the probability of observing at least one spurious interaction is high despite the lack of a biological or pharmacological basis for expecting an interaction. Thus, any interaction with a p-value below the 5% type I error level in the analysis of primary outcome will be interpreted as “flag” to prompt further investigation into the consistency of the pattern within secondary and related outcomes.

The analyses for the subgroups as defined in section 6.2.4 will also be performed based on the same analysis set and data scope as in the main analysis for the secondary efficacy outcomes (also the individual components).

6.2.10 Sensitivity analyses

To support the primary study results and to assess the robustness of the primary analysis, several sensitivity analyses will be performed.

The primary efficacy variable will be analyzed based on the ITT analysis set and ITT data scope

- using the Cox proportional hazard model with actual stratification
- using the Cox proportional hazard model without stratification
- Using a proportional hazards estimator that is robust to departures from proportional hazard (Boyd et al. 2012)

Statistical Analysis Plan

Protocol No.: **BAY 59-7939 / 17454**

Page: 25 of 36

The primary efficacy outcome (also the individual components) as adjudicated by ICAC will also be analyzed using the same Cox PH model as described in section [6.2.5](#) based on SAF and on-treatment data scope. The same analysis will be repeated based on ITT analysis set and overall study duration including post-study treatment follow-up. All subjects who are event free will be censored at the date of last clinical event ascertainment or last contact.

The primary efficacy outcome as reported by investigator will be analyzed similarly based on the ITT analysis set and ITT data scope.

For the individual components of investigator reported primary efficacy outcome see [Appendix E](#).

In addition, the secondary efficacy outcomes as adjudicated by ICAC (if applicable) will be analyzed using the same Cox PH model as described in section [6.2.5](#) based on the SAF and on-treatment data scope.

If the sensitivity analyses are much different from the primary analysis, additional analyses may be performed to further investigate the inconsistency.

Concordance of ICAC and investigator reports on the primary efficacy endpoint events will be provided for the combined treatment group.

Sensitivity analyses to address the potential impact of missing data

Although extensive effort will be made to reduce the number of subjects with missing follow-up, it is expected that there will be missing vital status and event information in some subjects. Subjects who are not followed up until the ECOD (consent withdrawal, objection to further data collection, and lost to follow up) before the development of primary efficacy events will be considered missing.

Sensitivity analyses will be performed for the primary efficacy endpoint based on the ITT analysis set and ITT data scope to evaluate the potential impact of missing data on analysis results and robustness of study conclusions.

To evaluate the plausibility of informative censoring, distributions of baseline demographics and other characteristics will be compared between subjects with and without missing data, taking into account treatment and regardless of treatment.

Potential impact of missing data will be evaluated by imputation, where the event process will be imputed in missing follow-up periods (ie. time from last clinical event ascertainment date until ECOD in subjects without a primary efficacy endpoint prior to the ECOD). The robustness of the treatment effect with respect to missing data will be evaluated with a tipping point analysis (see [Appendix C](#) for mathematical details). In this analysis, we will:

1. Estimate the hazard at time of loss to follow-up among subjects in ITT analysis set, adjusting for treatment group, stratification factors, and the following baseline covariates:
 - age (<65; \geq 65 to <75; \geq 75 years)
 - diabetes mellitus (yes, no)
 - prior coronary artery disease (yes, no)
2. Inflate the hazard only in the rivaroxaban group by a set of inflation factors; assuming non-informative censoring in the control group

Statistical Analysis Plan

Protocol No.: **BAY 59-7939 / 17454**

Page: 26 of 36

3. Perform simulations to impute events to the end of the study using standard multiple imputation rules, and compute the hazard ratio and two-sided 95% CI using the primary Cox proportional model
4. Given the study results is statistically significant in favor of rivaroxaban, increase the inflation factor (by repeating steps 2 and 3) until the upper limit of the two-sided 95% CI for the hazard ratio crosses 1.0; this will be the “tipping point”

The tipping point will show how much higher the event risk after drop-out would need to be in the rivaroxaban group so that statistical significance is lost.

In addition, the extent of missing information will be described by the fraction of subjects with missing data and the fraction of unobserved rivaroxaban or rivaroxaban placebo follow-up subject-years.

6.3 Pharmacokinetics/pharmacodynamics

Not applicable

6.4 Safety

6.4.1 Adverse events

Because the safety profile of rivaroxaban has been well established in previous large and extensive trials, this study will collect limited AE data. Adverse events (AEs) will be coded by Medical Dictionary for Regulatory Activities (MedDRA). The version number of MedDRA used for the analyses will be stored in the clinical database. A listing will be provided linking the original investigator terms and the coded terms.

Analyses of reported adverse events will be performed based on the SAF and on-treatment data scope.

In case of uncertainty (e.g., missing or incomplete dates), AEs will be classified as “treatment emergent” (TE) following the worst case approach.

An overall summary of AEs and treatment-emergent (TE) AEs (only considering study medication of rivaroxaban or rivaroxaban placebo) will be generated by treatment group and overall.

Incidence of subjects with treatment emergent adverse events (TEAEs), drug-related and/or serious TEAEs, and TEAEs causing discontinuation of study drug will be summarized by treatment grouped by MedDRA Primary System Organ Class (SOC) and Preferred Term (PT). In addition, the incidence of pre-treatment AEs and AEs during the post study treatment follow up will be tabulated.

Serious adverse events (SAEs), AEs leading to discontinuation and AEs of special safety interest (if applicable) will be listed. The date, relative day (to start of study medication) and phase of the study (pre-treatment, during treatment, post-treatment) will be included.

Further summaries of AEs by maximum intensity and worst outcome will be provided, consistent with Bayer Global Medical Standards.

Specific to Japan, outcome events (i.e. bleeding, efficacy outcome events) are reported as an (S)AEs as required by PMDA, thus (TE)AEs and SAEs will be further presented for Japan only subjects vs. non-Japan subjects.

Statistical Analysis Plan

Protocol No.: **BAY 59-7939 / 17454**

Page: 27 of 36

6.4.2 Primary safety variable

The primary safety variable is the time from randomization to the major bleeding events according to the thrombolysis in myocardial infarction (TIMI) classification, as defined in the ICAC charter.

6.4.3 Secondary safety variables

The secondary safety variables are:

- the time from randomization to the major bleeding events according to the International Society on Thrombosis and Haemostasis (ISTH) classification
- the time from randomization to the type 3b and above bleeding events according to the Bleeding Academic Research Consortium (BARC) classification

Bleeding definitions can be found in the ICAC charter.

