#### **9.6.1.3.1 Assessment of bleeding events**

Bleeding events, which are specific safety outcomes of this study, will be continuously monitored from signing of the ICF until post-study treatment follow-up visit.

All bleeding events will be reported on the designated bleeding reporting forms in the eCRF. Since bleeding events are recorded as safety outcome and the risk profile of rivaroxaban has been established in multiple previous studies, these events are not required to be recorded as an AE/SAE and thus are exempted from SAE reporting.

Bleeding occurring after randomization that is related to the index revascularization procedure (e.g. bleeding requiring an unplanned surgical take-back operation to manage) will also be reported, including details of the management of the bleeding event and any limb complications (e.g., resulting in major amputation or compartment syndrome requiring surgical management). These events will be reviewed by the IDMC on a regular basis and not reported as SAEs.

Potential major bleedings occurring after randomization will undergo adjudication by the ICAC. Major bleeding as adjudicated per TIMI classification is considered the primary safety outcome of the study, but other bleeding types (e.g., based on BARC and ISTH criteria) will also be evaluated as defined in the ICAC charter.

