#### **9.6.1.3.1.2 Secondary safety outcomes**

In addition to the TIMI classification, bleeding events will be assessed using the BARC and the ISTH classifications, as defined in the ICAC charter.

 This section was added with Protocol Amendment 4 because it was erroneously omitted from the original version (change no. 16).

 Text revised with Protocol Amendment 4 (change no. 17).

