### **9.6.1.3.3 Reporting of serious adverse events and study-specific exemptions - amended**

The common definition of SAEs is given in Section 9.6.1.1. Each SAE must be followed up until resolution or stabilization by submission of updated reports to the designated recipient.

The efficacy and safety outcomes in this study will be collected in the eCRF and regularly monitored by the IDMC during the entire course of the study in a timely adequate manner. Due to this targeted surveillance, no AE documentation and no expedited SAE reporting will be performed for these events. Consequently, they will neither be un-blinded nor reported to regulatory authorities, IECs, or investigators. The IDMC will periodically review and assess all safety data for imbalances in safety outcomes. It is believed that in this way patient safety can continue to be monitored throughout the duration of the trial, along with study integrity. If unexpected safety issues are identified, specific amendments will be implemented.

The following rules should be followed:

1. **Primary and secondary efficacy outcome events** occurring after randomization will not be recorded on the AE page and not be reported as SAEs to Sponsor's PV

 Cross-references added by Amendment 4 (change no. 17).

 Wording changed by Amendment 4 (change no. 17).

department, but they will be collected on the specific eCRF pages as an efficacy outcome event.

2. **Safety outcome events** (i.e., bleeding events occurring after signing of the ICF) will not be recorded on the AE page and not be reported as SAEs to Sponsor's PV department, but they will be collected on the specific eCRF pages as a safety outcome event.
3. **All other SAEs (including complications of efficacy or safety outcome events)** that fulfill the seriousness criteria provided in Section 9.6.1.1 need to be collected on the eCRF (AE page) and reported as SAEs to the PV department. All SAEs that fulfill SUSAR criteria will be reported to the concerned authorities by expedited means (see Section 9.6.1.4).
4. **Pregnancies** need to be captured and reported to the Sponsor's PV department within 24 hours, even if classified as non-serious (see Section 9.6.2).

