### 10.3.3.3 Analysis of safety outcomes and regular adverse events

Time to the first occurrence of the primary safety outcome (i.e., TIMI major bleeding) will be compared using a Cox proportional hazards model stratified by type of procedure and clopidogrel use with treatment group as a covariate. The analysis will be conducted in the safety analysis set and for the on-treatment data scope. The other time-to-event safety outcomes will be analyzed similarly.

Adverse events reported as per study-specific rules for event exemption (Section 9.6.1.3) will be analyzed by MedDRA system organ class and preferred term level using tabulated summaries with absolute and relative frequencies.

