ISTH major bleeding BARC type 3b and above bleeding	Main	SAF	On-treatment	On-treatment	Stratified Cox PH model, KM plot

Note: Details of the planned analyses are provided in section 6.

1. Intention-to-treat (ITT) analysis set – all randomized subjects. Treatment assigned as randomized; Safety analysis set (SAF) – all randomized subjects who received at least one dose of study medication. Treatment assigned as treated. See section 5.1 for details.
2. ITT data scope – all outcome events observed from randomization until efficacy cut-off date; On-treatment data scope – all outcome events observed from randomization until 2 days following permanent discontinuation of the study drug (rivaroxaban or rivaroxaban placebo). See section 4.5.2 for details. Overall study duration scope - all outcome events observed post randomization including post-study treatment follow-up.
3. See section 4.5.3 and [Appendix A](#) for details regarding the censoring rules according to each data scope.
4. Not stratified for subgroups related to type of procedure and clopidogrel use. See sections 6.2.4, 6.2.9 and 6.4.5 for details.

6. Statistical Methodology

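### SAP 6.4 names no by-arm comparison of any or lesser bleeding, although all bleeds are collected and, outside Japan, kept off the adverse event page

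*SAP*

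**What the plan says.** **Collection.** Protocol 9.6.1.3.1 states: "All bleeding events will be reported on the designated bleeding reporting forms in the eCRF". Central review covers less: "Potential major bleedings occurring after randomization will undergo adjudication by the ICAC". Protocol 9.6.1.3.3, rule 2, takes safety outcome events out of adverse event recording: "i.e., bleeding events occurring after signing of the ICF) will not be recorded on the AE page". They are also not sent to the sponsor's pharmacovigilance group as SAEs. SAP 6.4.1 notes one exception: in Japan, bleeding and efficacy outcome events are reported as (serious) adverse events.

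**Classification.** Protocol 9.6.1.3.1 makes TIMI major bleeding the primary safety outcome and adds that "other bleeding types (e.g., based on BARC and ISTH criteria) will also be evaluated as defined in the ICAC charter". Under secondary safety outcomes, Protocol 9.6.1.3.1.2 says: "In addition to the TIMI classification, bleeding events will be assessed using the BARC and the ISTH classifications, as defined in the ICAC charter". Neither sentence names a grade. Protocol 10.3.3.3 sets a stratified Cox model for TIMI major bleeding, on the safety analysis set and on-treatment scope, and continues: "The other time-to-event safety outcomes will be analyzed similarly".

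**Analysis.** SAP 6.4.2 names TIMI major bleeding. SAP 6.4.3 names ISTH major bleeding and "the time from randomization to the type 3b and above bleeding events according to the Bleeding Academic Research Consortium (BARC) classification". The secondary safety row of SAP Table 1 reads "ISTH major bleeding BARC type 3b and above bleeding". SAP 6.4.4 adds only vital signs. SAP 6.4.5 applies the Cox model to the primary and secondary variables.

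**The concern.** The stated safety objective is overall safety and tolerability, and Protocol 3.4 identifies bleeding as the main risk of the drug. In many trials a reader who wanted to see lesser bleeding by arm could turn to the adverse event tables. Here the recording exemption removes that backstop outside Japan. A bleed that led to hospitalization but met none of the three definitions would, as a bleed, be absent from the SAE tables outside Japan. It would also be absent from every by-arm bleeding comparison named in SAP 6.4.

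At stake is whether the final report, prepared from the SAP as written, shows how much lesser bleeding the added drug causes. The efficacy conclusion and the TIMI major bleeding result are not affected.

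**Working it through.** The point is textual. The plan states no sample size, power or expected rate for bleeding, so there is no figure to reproduce; the 1,015-event target concerns efficacy only. The check is an inventory.

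**1. Bleeding variables in SAP 6.4.2 to 6.4.3.** TIMI major (1) + ISTH major (1) + BARC 3b and above (1) = 3. Cut at major or 3b and above: 3 of 3. Any or non-major bleeding: 0.

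**2. Safety rows in SAP Table 1.** TIMI major: main 1 + supportive 2 + subgroup 1 = 4. ISTH major and BARC 3b and above share 1 row. Total 4 + 1 = 5, all cut at major or 3b and above. These rows reuse the same three variables, so they confirm step 1 rather than add to it.

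**3. Other bleeding outputs in SAP 6.4.5.**
- The count of subjects with multiple bleeds, the landmark analysis and the concordance summary all concern TIMI major bleeding.
- Bleeding leading to permanent discontinuation has no severity cut, but it is laid out by bleeding site and no treatment arm is mentioned.

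**4. Adverse event tables in SAP 6.4.1.** These are by treatment group. Under Protocol 9.6.1.3.3 they do not carry bleeds as such outside Japan.

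**5. Indirect routes by which lesser bleeding could still show.**
- SAP 6.1.1 tabulates primary reasons for permanent discontinuation by arm. This reaches only bleeds that ended treatment.
- Japanese adverse events (SAP 6.4.1). This covers one country.
- Serious complications of safety outcome events, which Protocol 9.6.1.3.3, rule 3, sends to the adverse event page as SAEs. This shows consequences of bleeds, not the bleeds.
- Resource-use data (Protocol 9.7.3), which may include bleeding-related visits. SAP 6.5 says only that additional analyses may be performed and reported separately.
- The benefit-risk analysis (SAP 6.6), which compares arms on TIMI-classified bleedings with no stated severity limit. Its details are in a separate document, and it is not meant for hypothesis testing.

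**6. Result.** Named by-arm analyses of any or lesser bleeding within SAP 6.4 and Table 1: 0. Outside them, the routes in step 5 are partial or unspecified.

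**7. What the fix needs.** The data exist, since all bleeds are on dedicated forms. The method exists in Protocol 10.3.3.3 and SAP 6.4.5. Adjudication does not extend to most of the added events.

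**The case against.** **The protocol leaves the choice of grades open.** Both protocol sentences on BARC and ISTH defer to the ICAC charter, which is not among the documents. The sentence in 9.6.1.3.1 directly follows the one on adjudicating potential major bleeds, so BARC and ISTH grading may have been meant only for those. Assessing events with a classification is not a promise to compare every grade between arms, and detailing analyses is the SAP's job. This stands. A reader might infer that the SAP has narrowed the protocol's secondary safety outcomes; the documents do not support that, because the charter may define exactly the grades the SAP uses. Nor does the absence of section 6.4.3 from the SAP's document history help: that history lists changes between SAP versions, so silence proves little.

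**More may be planned than the safety section names.** SAP 5.1.2 says the planned analyses are not limited to Table 1, and output titles and mock-ups are in a separate TLF specification (SAP 1). SAP 4.5.3 calls the on-treatment analysis the primary one for time to bleeding events, without a severity limit. The first two points stand as limits. The third sets a censoring rule and defines no variable.

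**Targeted safety collection was deliberate, and the IDMC watches for imbalances.** True, but IDMC review protects patients during the trial; it does not pre-specify what the final report compares.

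**An any-bleeding analysis would rest mainly on unadjudicated events.** Also true. It is a reason to label the result and keep it supportive, not to leave it out. SAP 6.2.6 and 6.2.7 already accept investigator-reported efficacy events where none were adjudicated.

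**Conclusion.** The point holds as a cheap improvement. Within SAP 6.4 and Table 1, 3 of 3 bleeding variables and 5 of 5 safety rows stop at major or BARC 3b and above, and no named by-arm analysis covers any or lesser bleeding. Because bleeds stay off the adverse event page outside Japan, the safety section taken alone leaves the overall safety and tolerability objective incompletely answered. The practical effect cannot be sized without bleeding rates.

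The conclusion assumes that the report follows the SAP text and that the TLF specification does not already add such a table. It should not be stretched to say that lesser bleeding is uncollected or will never be reported: collection is explicit, and the partial routes listed above exist. No primary or secondary analysis is shown to be wrong.

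**What to change.** In SAP 6.4.3, 6.4.5 and Table 1, add any reported bleeding as a supportive safety variable. Analyse it on the safety analysis set and on-treatment scope, giving the number of patients by arm and the stratified Cox hazard ratio. Label events as investigator-reported where they were not adjudicated. In SAP 6.4.5, state that bleeding leading to permanent discontinuation is presented by treatment group.

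The cost is one added variable and a few lines of SAP text. It needs no new data collection, no new method and no alpha, and the primary analysis is unchanged. The downside is that most added events will not have been adjudicated, so the result can support the three existing variables but not replace them.
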